- 19. During sub-study 2 of study stage 2, fecal culture/microscopy (including fecal culture, clostridium difficile toxin, parasites ovas and parasites) may also be performed if the subject's status requires it.
- 20. Colonoscopy will be performed at visit 11 in study stage 1 to obtain the Mayo endoscopic subscore and complete Mayo score of the subjects and to determine their eligibility. Colonoscopies will also be performed at week 48 (end of the study visit or early termination visit).
- 21. On the days of visits during the study treatment period, the investigational product will be taken at the study sites and the time of administration will be recorded according to the study flow chart.
- 22. Mayo score: the complete Mayo score is calculated from the stool frequency, rectal bleeding, endoscopic findings, and physician overall evaluation; The adapted Mayo score is calculated from stool frequency, rectal bleeding, and physician overall evaluation.
- 23. Review of subject diaries: subject diary review is required for all visits from visit 12 to the end of the study/early termination visit.
- 24. The IBDQ is to be completed by the subjects at week 24 and 48 or early termination visit.

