In sub-study 2, if subjects have not achieved clinical response yet at week 24, they will be required to terminate treatment and withdraw from the study. In addition, for all subjects who enter the study stage 2, if the investigator judges that they are not benefiting from the study treatment, or present with disease progression during the study period, or need for surgical intervention for UC treatment, the investigational treatment should also be terminated.

9) Others

Note: Specific reasons should be recorded in the eCRF. The investigator should do their utmost to determine the primary reason of withdrawal, and if possible, document it (e.g., withdrawal due to AEs or treatment failure).

5.4.5. Criteria for termination of the clinical study.

The study may be terminated prematurely in case of the following:

- The principal investigator and sponsor believe that the number and severity of AEs indicate that the study must be terminated.
- Newly obtained data raise concerns about the safety of the investigational product: continuation of the study may pose a risk to subjects.
- The principal investigator and sponsor believe that a flawed study design or unplanned unblinding has impaired the integrity of the study, thereby making it impossible to evaluate the efficacy and safety of the investigational product.

The premature termination of the study must be determined and recorded by the principal investigator in consultation with sponsor. Study results must be reported as far as possible according to the protocol requirements.

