7.2.2. Colonoscopy

In study stage 1, colonoscopy will be performed to obtain a Mayo endoscopic subscore and a complete Mayo score and then determine subject eligibility within 14 days prior to randomization during screening period. Colonoscopy will also be performed at week 12 (or early termination). Besides, subjects who enter study stage 2 will undergo colonoscopy at week 24 (only for sub-study 2) and week 48 (or early termination visit).

To ensure data quality and standardization, each study site should examine with the same colonoscope throughout the clinical study wherever possible, and all the colonoscopic results will be centrally read and evaluated. All the colonoscopy examinations should be performed by a properly trained endoscopist to complete colonoscopy at each site, and the same endoscopist should be used for a certain subject throughout the study wherever possible. If impossible, it is required to record the exact name of the endoscopist responsible for each colonoscopy.

For the information on requirements for colonoscopy and evaluation by the central reader, see the relevant operating document.

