7.2.3.2 Adapted Mayo score

Adapted Mayo score will be calculated based on the above items1, 2 and 3 (stool frequency, rectal bleeding, endoscopic findings). The adapted Mayo score will be calculated at the visit at screening and week 12 (or early termination visit) during study stage 1 as well as at week 24 (only sub-study 2) and week 48 (or early termination visit) during study stage 2.

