9.13. Interim analysis

One interim analysis will take place for this study once all the subjects have completed week 12 (visit 11, last dose/early discontinue visit) in stage 1, the unblinded study team will carry out the analysis on primary efficacy endpoint after database lock. The primary efficacy endpoint is the change in adapted Mayo score from baseline at week 12 compared between CBP-307 0.2 mg and placebo in stage 1 while the stage 2 analysis will be exploratory, and no α reserved for stage 2. Exclusive of primary efficacy analysis in stage 1, all other comparative analysis results of the treatment groups and the placebo group are used for exploratory purpose.

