6.2. BASELINE

For stage 1: Unless otherwise specified, baseline is defined as the last non-missing measurement taken prior to the first treatment date (including unscheduled assessments) in stage 1. In the case where the last non-missing measurement and the reference start date coincide, and no time collected, that measurement will be considered pre-dose, except that the protocol specifies the measurement is post-dose.

For subject randomized but not treated, baseline is defined as the last non-missing measurement on or before randomization date.

For subjects entered into stage 2 sub-study 1: the baseline will be the same as in stage 1.

For subjects entered into stage 2 sub-study 2: the baseline is defined as the last non-missing measurement taken prior to the first treatment date (including unscheduled assessments) in stage 2 sub-study 2.

For all stages (0.2mg only) analysis, baseline will be the same as in stage 1.

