Adapted Mayo score is calculated based on the above assessment 1, 2 and 3 (Stool frequency, Rectal bleeding and Endoscopic findings). The Adapted Mayo score will be calculated at the visit at screening and week 12 (or early termination visit) during stage 1 study as well as at week 24 (only sub-study 2) and week 48 (or early termination visit) during stage 2 study.

Partial Mayo scores

Partial Mayo scores will be calculated at weeks 2, 4, 8 and 12 (i.e., Mayo score without colonoscopy findings) in study stage 1. In sub-study 1 of study stage 2, partial Mayo scores will be calculated at weeks 18, 24, 32 and 40. In sub-study 2 of study stage 2, partial Mayo scores will be calculated at weeks 16, 32 and 40.

Partial Mayo scores will be calculated based on assessment in the items 1, 2, and 4 of section 14.1.1 (Stool frequency, Rectal bleeding and Physician's global assessment).

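### Stage 2 flow-chart notes build the adapted Mayo score from the physician's assessment instead of endoscopy, against protocol 7.2.3.2 and SAP 14.1

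*Protocol*

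**What the plan says.** **The stage 2 notes.** Table 3 note 20 (sub-study 1) and Table 4 note 22 (sub-study 2) carry the same sentence: "The adapted Mayo score is calculated from stool frequency, rectal bleeding, and physician overall evaluation".

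**The definitions.** Protocol 7.2.3.2: "Adapted Mayo score will be calculated based on the above items1, 2 and 3 (stool frequency, rectal bleeding, endoscopic findings". SAP 14.1: "Adapted Mayo score is calculated based on the above assessment 1, 2 and 3 (Stool frequency, Rectal bleeding and Endoscopic findings". Both sections go on to list week 24 (sub-study 2 only) and week 48. Protocol 7.2.3.3 assigns items 1, 2 and 4 to the partial score. The Table 4 grid keeps the two scores on separate rows: adapted at weeks 24 and 48, partial at weeks 16, 32 and 40.

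**The stage 1 chart.** Table 2 note 23 gives the adapted score with endoscopy. Its bracket for the partial score cites items 1, 2 and 4 but then names endoscopic findings.

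**Week 24 colonoscopy.** Table 4 note 20 mentions visit 11 and then: "Colonoscopies will also be performed at week 48 (end of the study visit or early termination visit". Protocol 7.2.2 says that "subjects who enter study stage 2 will undergo colonoscopy at week 24 (only for sub-study 2) and week 48 (or early termination visit".

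**Use of the week 24 result.** Protocol 5.4.4, for sub-study 2: "if subjects have not achieved clinical response yet at week 24, they will be required to terminate treatment and withdraw from the study".

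**Endoscopy reader.** Protocol 9.12 takes the endoscopic score of the clinical center for efficacy. If data are lost, the investigator's read stands in as an SES-CD score. Protocol 7.2.2 has every colonoscopy read centrally. SAP 14.3.2 uses the central read, with the investigator's read if the central one is missing.

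**Endoscopic grade 1.** SAP 14.1 includes mild friability; protocol 7.2.3 lists friability only from grade 2. SAP 3.3 does not declare the difference.

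**The concern.** The notes give the adapted score the composition of the partial score and erase a distinction that the Table 4 grid makes. The sentence stands in both stage 2 charts, and protocol section 7 sends readers to those charts for visit details. The supplied text has no rule saying which part of the protocol prevails.

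Two things are at stake. First, the exploratory stage 2 endpoints that rest on the adapted score: response and change in score at weeks 24 and 48. Second, and more practically, the week 24 call in sub-study 2. Non-response there ends treatment under protocol 5.4.4, and response starts steroid tapering under protocol 6.6.1. If sites and analysts score by different items, the call acted on and the call analysed can disagree for the same subject.

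The 9.12 wording, read literally, points to a different reader from protocol 7.2.2 and the SAP. The grade 1 wording leaves the protocol and SAP with two endoscopic scales.

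**Working it through.** **Design figure tied to this score.** Protocol 9.2 and SAP 7.4 assume a difference of 1.2, SD 2.0, two-sided alpha 0.05, power 80% and 15% dropout.

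- n per arm = 2 × (1.960 + 0.842)² × (2.0/1.2)² = 43.6, so 44 evaluable.
- 44 / 0.85 = 51.8, so 52 per arm, as stated.

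This rests on the week 12 score, which Table 2 note 23, protocol 7.2.3.2 and SAP 14.1 all define with endoscopy. Correcting the stage 2 notes changes nothing here.

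**Response rule** (protocol 9.8.1, SAP 14.3.1). The total falls by at least 2 points and at least 30%, and rectal bleeding either falls by at least 1 point or ends at 1 or below.

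**Reference visit.** For sub-study 2, SAP 6.2 says "baseline is defined as the last non-missing measurement taken prior to the first treatment date (including unscheduled assessments) in stage 2 sub-study 2", which in practice is the week 12 assessment.

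**Assumed starting state.** Stool 2, bleeding 2, endoscopy 3, PGA 2. Items 1, 2, 3 give 2 + 2 + 3 = 7; items 1, 2, 4 give 2 + 2 + 2 = 6. The state is illustrative, not trial data.

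| Week 24 (stool/bleeding/endoscopy, PGA) | Items 1, 2, 3 | Items 1, 2, 4 |
|---|---|---|
| 2/1/3, PGA 1 | 7 to 6: fall 1, 1/7 = 14.3%, non-response | 6 to 4: fall 2, 2/6 = 33.3%, response |
| 2/1/1, PGA 2 | 7 to 4: fall 3, 3/7 = 42.9%, response | 6 to 5: fall 1, 1/6 = 16.7%, non-response |

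Bleeding goes from 2 to 1 in both rows, so the bleeding condition is met throughout and only the choice of third item decides the call.

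**Mixed case.** Suppose the week 12 reference stays on items 1, 2, 3 (as Table 2 note 23 has it) and only week 24 follows note 22. Row 1 becomes 7 to 4 (3/7 = 42.9%, response) and row 2 becomes 7 to 5 (2/7 = 28.6%, non-response). Both still differ from the endoscopy-based call.

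**Reference-visit check.** A subject with this state at both stage 1 baseline and week 12 is a week 12 non-responder and gives the same results whichever visit is the reference.

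**Reader and grade wording.** These can only be compared as text. Protocol 6.1.3 uses the term clinical center for the site, so the literal sense of 9.12 is a site score. SES-CD appears nowhere else in the supplied documents. SAP 9 lists both an investigator and a central endoscopy score, so there are two values to choose between.

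**The case against.** The strongest reply is that 7.2.3.2 and SAP 14.1 are the defining sections, agree with each other, name the stage 2 visits and govern the derivation, so the notes are a slip with partial-score items in the wrong place. That probably describes how the error arose, and it is why no effect on the data is asserted. It does not dispose of the point. The supplied SAP is dated 18 January 2023, after the planned study end of September 2022, so on the planned timeline site calls rested on the protocol, which holds both definitions.

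It is also fair that protocol 5.4.4 says only clinical response, without naming the score. That the adapted score is meant is an inference from the sub-study headings in protocol 5.1, which sort subjects by adapted-score response. In sub-study 1, withdrawal for recurrence uses the partial score, so Table 3 note 20 drives no continuation decision.

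Four stronger readings might be inferred, and the documents do not support them:

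- *Week 24 went without endoscopy.* Table 4 note 20 omits week 24 but does not exclude it. The Table 4 grid, protocol 5.1 and 7.2.2, and SAP 3.1 all provide for colonoscopy at week 24. Note 22 itself includes endoscopy in the complete score, which the grid requires at week 24.
- *The SAP's grade 1 contradicts its remission rule.* That rule requires an endoscopy subscore of 1 or less, excluding friability. The exclusion can sensibly limit a grade that allows mild friability, so the two are compatible.
- *Site reads replaced central reads.* Protocol 9.12 is probably a wording slip; 7.2.2 and SAP 14.3.2 both point to central reading.
- *A known share of subjects was misclassified.* The documents give no joint distribution of the items. Counts of discordant score combinations depend on the starting states chosen and weight every combination equally, although protocol 7.2.3 has the PGA take account of the other items.

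**Conclusion.** The conflict is real: two stage 2 notes state a scoring rule that differs from protocol 7.2.3.2 and SAP 14.1, and following them can reverse a response call in either direction. The two worked cases prove that reversal is possible; they rest on assumed scores and say nothing about how often it happened.

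The reach is limited. Protocol 9.13 says that "the stage 2 analysis will be exploratory" and reserves no alpha for it. The notes do not touch the week 12 primary endpoint, sub-study allocation at week 12, the 52 per arm or the power. What lifts the point above a typing error is the week 24 call in sub-study 2, on the inference that it uses the adapted score. The passages must be reconciled.

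The reader wording in 9.12 is a secondary conflict. It bears on every endoscopy-based score, but SAP 14.3.2 supplies one clear rule and no effect on data is shown. The grade 1 difference is minor: an undeclared mismatch between protocol and SAP, with no contradiction of the remission criterion and no effect on data claimed.

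**What to change.** 1. Align Table 3 note 20 and Table 4 note 22 with protocol 7.2.3.2 and SAP 14.1 (items 1, 2 and 3).
2. In Table 2 note 23, correct the partial-score bracket to the physician's global assessment, matching the items it cites.
3. Reconcile Table 4 note 20 with the Table 4 grid and protocol 7.2.2 on the week 24 colonoscopy.
4. Confirm which items produced the week 24 and week 48 adapted scores and the week 24 response calls. Re-derive scores only if they came from the notes.
5. Replace the reader sentences in protocol 9.12 with the SAP 14.3.2 rule and remove the SES-CD reference.
6. Make the endoscopic grade tables in protocol 7.2.3 and SAP 14.1 match the grading that the central reader applied. If that grading allows mild friability at grade 1, declare it in SAP 3.3 and state how remission excludes it.

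The cost is text corrections or a note to file, one check of the central reading document and one check of the items used at weeks 24 and 48. No new data, sample size change or change to the primary analysis is needed.

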2 ETHICAL CONSIDERATIONS

2.1. Regulatory and Ethical considerations

This study will be conducted in accordance with the protocol and with the following:

- Consensus ethical principles derived from international guidelines including the Declaration of Helsinki and Council for International Organizations of Medical Sciences (CIOMS) International Ethical Guidelines.
- Applicable ICH Good Clinical Practice (GCP) Guidelines.
- Applicable laws and regulations.

Before the study starts, the investigator is required to submit the Protocol, Protocol Amendment, Investigator's Brochure, Informed Consent Form (ICF) and other relevant documents such as recruitment advertisements (if applicable) to the Independent Ethics Committee (IEC)/Institutional Review Board (IRB) for approval. All correspondence with the IEC/IRB needs to be kept in the Investigator Site File (ISF). A copy of the approval letter issued by the IEC/IRB approval needs to be submitted to sponsor. The study can only be started after approved by the IEC/IRB.

If the protocol needs to be amended during the study, the revised protocol should be submitted to the IEC/IRB for approval before the implementation of the protocol amendment. If new important information involving investigational product is obtained, ICF must be revised and then submitted to the IEC/IRB in written form for review and approval. The subjects must be informed of the update and re-consented to the most current, approved ICF version.

The Investigator will be responsible for the following:

- Providing written summaries of the status of the study to the IRB/IEC annually or more frequently in accordance with the requirements, policies, and procedures established by the IRB/IEC.
- Notifying the IRB/IEC of SAEs or other significant safety findings as required by IRB/IEC procedures.
- Providing oversight of the conduct of the study at the study center and adherence to requirements of 21 CFR, ICH guidelines, the IRB/IEC, European regulation 536/2014 for clinical studies (if applicable), and all other applicable local regulations.

After reading the protocol, each investigator will sign the protocol signature page and send a

copy of the signed page to the sponsor or representative. The study will not start at any study center at which the investigator has not signed the protocol.

2.2. Subject information and the Informed Consent Form

Sponsor will not obtain the name of the subjects. The subject's number will be recorded in the electronic case report form (eCRF). If the subject's name appears in any document (such as a laboratory test report), the name must be erased from the copy of the document to be submitted to sponsor. The study data must be stored in computers in accordance with local regulations for data protection. It is required that subjects be informed that clinical quality assurance auditors, the IEC/IRB, the regulatory authority, or other authorized personnel appointed by the sponsor may review their medical records to verify the collected data and that all personal information for review will be kept strictly confidential in accordance with local regulations for data protection.

The investigator will keep a subject identification code list (containing the subject's number and corresponding name), so that subject records can be identified.

Informed consent must be obtained from a subject before the start of any study procedures. Subjects must be informed that their participation is voluntary. Subjects or their legally authorized representative will be required to sign a statement of informed consent that meets the requirements of 21 CFR 50, local regulations, ICH guidelines, Health Insurance Portability and Accountability Act (HIPAA) requirements, where applicable, and the IRB/IEC or study center. The medical record must include a statement that written informed consent was obtained before the subject was entered in the study and the date the written consent was obtained. The authorized person obtaining the informed consent must also sign the ICF. Subjects must be re-consented to the most current version of the ICF(s) during their participation in the study. A copy of the ICF(s) must be provided to the subject or the subject's legally authorized representative.

Subjects are required to sign an updated ICF before entering the study stage 2.

3 STUDY BACKGROUND

3.1. Overview of ulcerative colitis

Inflammatory bowel disease (IBD) is a type of intestinal inflammatory disease that includes ulcerative colitis (UC) and Crohn's disease (CD). The cause of IBD is unknown. UC is a chronic non-specific inflammatory disease of the rectum and colon. The lesion is characterized by diffuse and superficial inflammation of the colonic mucosa. It is located mostly in the rectosigmoid colon, but can extend to the entire colon.

The clinical manifestations of UC include diarrhea, bloody purulent stool, and abdominal pain.

Protocol No.: CBP-307CN002 Confidential

Systemic features of UC, such as fever, weight loss, weakness, and hypoproteinemia, mostly appear in patients with moderate to severe UC. Extra-intestinal manifestations such as uveitis, arthritis, ankylosing spondylitis, or primary sclerosing cholangitis may also be seen in association with UC. Most of the patients show a chronic course of recurrent episodes, alternating with remission, and the symptoms of some patients are persistent and gradually worsening. Patients with IBD are at a higher risk of colorectal cancer.

In recent decades, the incidence of UC in Asia and the world has tended to increase persistently. The prevalence of UC in the United States, Western Europe, and Japan is approximately 200/100,000, 150/100,000 and 63.6/100,000, respectively. It is estimated that the prevalence of UC in China has reached 11.6 cases per 100,000 person-years. Although the prevalence in China is lower than in Western countries, it increases rapidly: an analysis of 10218 UC cases in China suggests that the prevalence of UC increased by 3.08 times from 2506 cases in 1980s to 7512 cases in 1990s.

3.2. Drug overview, structure and physicochemical properties

CBP-307 is a novel sphingosine-1-phosphate receptor subtype 1 (S1P1) modulator. It works by blocking the egress of T cells out from lymph nodes and thereby reducing their entry into intestinal tissues to exacerbate inflammation.

The active pharmaceutical ingredient (API) of CBP-307 is a white or off-white crystalline powder.

Name of the compound: CBP-307

Chemical formula: C₂₃H₂₄FN₃O₃•1/2 H₂O

Molecular weight: 418.46

Chemical name: 1-(2-fuoro-4-(5-(4-isobutylphenyl)-1, 2, 4-oxadiazol-3-yl) benzyl) azetidine-

3-carboxylic acid 1/2 hydrate

Chemical structure:

Figure 3. Chemical structure of CBP-307

3.3. Nonclinical pharmacology, pharmacokinetics and toxicology

3.3.1. Nonclinical pharmacology

In vitro and in vivo pharmacology

CBP-307 is a highly potent and specific second-generation S1P1 agonist. The sponsor has conducted a series of in vitro cell-based assays (i.e., compound-induced changes in the levels of intracellular cyclic adenosine monophosphate (cAMP) and β -arrestin, and S1P receptor internalization) to verify the activity and selectivity of CBP-307. The test results showed that CBP-307 increased the levels of cAMP and β -arrestin in S1P1-expressing cells with half maximal effective concentrations (EC50) of 0.09 nM and 0.67 nM, respectively, whereas it had no effect on S1P3, a S1P receptor subtype known to induce fibrosis in human and animal tissues. The sponsor also evaluated the effect of CBP-307 in the induction of internalization of S1P receptors expressed in Chinese hamster ovary (CHO). Data show that CBP-307 effectively induced the internalization of S1P1 with an EC50 of 7.05 nM and S1P5 with an EC50 of 22.21 nM.

CBP-307 activates and induces S1P1 internalization, thereby inhibiting the migration of lymphocytes from lymph nodes in animals and humans and thus reducing the number of lymphocytes in the peripheral blood. When CBP-307 0.1 mg/kg, 0.1 mg/kg and 0.3 mg/kg was orally administered to rats, mice and beagle dogs, respectively, it reduced the number of lymphocytes in the peripheral blood of these animals by more than 50%. This effect was dose-dependent and reversible. The numbers of lymphocytes in the peripheral blood of animals typically returned to the pre-dose level 12-48 hours after a single dose.

Safety pharmacology

The results of safety pharmacology studies that meet the requirements of Good Laboratory Practice (GLP) for Nonclinical Laboratory Studies showed that oral administration of CBP-307 50 mg/kg has no effect on the respiratory function of beagle dogs, and CBP-307 100 mg/kg has no effect on central nervous system (CNS) functions in SD rats. Cardiovascular safety studies showed that CBP-307 50 mg/kg caused a slight increase in diastolic blood pressure in

female beagle dogs within 1 to 3 hours after administration, and it had no effect on ECG parameters, including heart rate, RR interval, PR interval, QRS duration, QRS voltage, QT interval, QTcF interval, Tp-e interval, ST voltage and systolic blood pressure.

CBP-307 30 μ M does not inhibit the activity of any major human cytochrome P450 enzymes including 1A2, 2C9, 2C19, 2D6, 3A4, 2B6 and 2C8, thus CBP-307 is unlikely to interact with other drugs metabolized by the P450 enzymes. Besides, it was found that CBP-307 10 μ M had only 12% inhibitory effect on astemizole, which was able to bind to the hERG potassium channel (expressed on the surface of HEK cells). Such finding indicates that the potential of CBP-307 to cause QT prolongation in human is very low.

